5.3 Pharmacokinetic Evaluation: N/A

6.0 STATISTICAL CONSIDERATIONS

6.1 Primary Endpoint

Differences in CDRS-R and HAM-D scores will be divided by the standard deviation for effect size (which will not be scaled for statistical significance given the sample size). Descriptive statistics and repeated ANOVA will be used to evaluate efficacy. Tolerability will be evaluated examining safety and adverse events at every study visit. Given the novelty and duration of treatment, it is more likely 5 patients will be able to participate and provide enough data for future research that is funded to expand sample size.

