Safety Evaluations	
 Evaluations of CDRS-R (Children's Depressive Rating Scale Revised) and HAM-D (Hamilton Depression rating scale) scores will be used to measure efficacy. MMSE, Trails B, list generation, Columbia Suicide Scale, semi-structured interviews for Non-suicidal Self Injurious Behavior (NSSIB), and medical review will be used to evaluate safety. Assessment of the number and per cent treatments completed and number and percent of subjects who withdraw from treatment will be used to assess feasibility In addition, a medical review of symptoms, vital signs, UDS (Urine Drug Screen), physical exam, and applicable pregnancy test, regular assessment of adverse events and change in pregnancy status will be obtained.
Statistical And Analytic Plan	
This is a pilot feasibility study, and it will not be powered to show significance.
 
 We will compare pre- and post-treatment measures of depression in all subjects with repeated ANOVA measures Cognitive scales and safety assessments Descriptive statistics Pearson's r coefficient for correlation between Non-suicidal Self Injurious Behavior (NSSIB), depression, and suicidality changes

throughout the study.

- *The study may provide important preliminary data for NIH R01 applications.*

Data And Safety Monitoring Plan	PI is responsible for data quality management and ongoing assessment of safety
----------------------------------------	--------------------------------------------------------------------------------

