In this study we will investigate the **efficacy and durability** of the effects of iTBS in adolescent depression (see Specific AIM 1 below) by measuring changes in clinical ratings [CDRS-R, HAM-D, and Non-suicidal Self Injurious Behavior (NSSIB) evaluations] before and after 4 weeks of treatment, as well as 12 weeks following treatment. We expect that subjects will show: improvement in symptoms over 20 iTBS sessions as measured by the Children's Depression Rating Scale Revised (CDRS-R), HAM-D and Non-suicidal Self Injurious Behavior (NSSIB) measures, and persistence of this reduction of depressive symptoms through the 12 weeks follow up period of the study. In this study, we will investigate the **safety** of the effects of iTBS in adolescent depression (see Specific Aim 2 below). We will investigate safety of the treatment regimen by assessing suicidality. We expect suicidal thoughts and behavior will reduce with iTBS treatment as measured by the Columbia Suicide Severity Rating Scale (C-SSRS) and a psychiatrist's clinical assessment. We also expect that those with NSSIB at the start of the trial will have less after iTBS treatments. We do not expect any change in cognition measured with MMSE, Trails B, and list generation. We will investigate treatment feasibility by assessing treatment completion and withdrawal (See Specific Aim 3 below). We define the feasibility of iTBS will be defined as feasible by as completion of 15/20 (75%) iTBS treatment sessions by all subjects **AND** withdrawal from treatment of no more than one of five subjects (20%) due to intolerable side effects or persistent symptoms of

MDD. Investigation of efficacy, durability, safety as well as feasibility simultaneously is essential in this preliminary study of the use of iTBS in adolescents in order to justify a larger future study.

Non-Clinical and Clinical Study Findings

Potential Risks:

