2.0 STUDY OBJECTIVE

The purpose of the study is to determine the efficacy/durability, the safety, and the feasibility of iTBS in 5 adolescents with MDD.

Specific Aims.

Aim 1. Investigate the efficacy and durability of effects by estimating the magnitudes of pre-regimen vs. post-regimen longitudinal changes in CDRS-R, HAM-D, and NSSIB evaluations.

Hypothesis 1: Adolescents with MDD will show improvement in symptoms over 20 iTBS sessions as measured by the Children's Depression Rating Scale Revised (CDRS-R), HAM-D and NSSIB measures.

Hypothesis 2: Adolescents with MDD will show reduction of depressive symptoms will persists through the 12 week follow up period of the study.

Hypothesis 3: Adolescents with MDD who demonstrate NSSIB at the start of the trial will show reduction in NSSIB after iTBS treatments.

Aim 2. Investigate safety of the treatment regimen by assessing suicidality with the Columbia Suicide Severity Rating Scale (C-SSRS).

Hypothesis 1: Adolescents with MDD will show reduction in suicidal thoughts and behavior with iTBS treatment as measured by the Columbia Suicide Severity Rating Scale (C-SSRS) and a psychiatrist's clinical assessment.

Aim 3. Investigate treatment feasibility by assessing treatment completion and withdrawal.

Hypothesis 1: iTBS will be considered feasible if: a.) 15/20 (75%) iTBS treatment sessions are completed by all subjects, and; b.) no more than one of five subjects (20%) withdraw from iTBS due to intolerable side effects or persistent symptoms of MDD.

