3.0 INVESTIGATIONAL PLAN (brief overview)

3.1 Study Design

Type of design: A pilot study that is an open label, feasibility study. This study will aim to reduce depressive symptoms in adolescents using iTBS and evaluating the safety of methods. This will be an uncontrolled study design.

The study phases are described below:

- **Screening/Baseline:** This will include informed consent, an Intake Assessment (including psychological assessments / questionnaires), medical review with physical exam, vitals, UDS, and pregnancy screening for a total of about 2 hours, and needed collateral. Screening will last up to 1 week prior to scheduling first treatment session in order to allow sufficient time to gather all needed medical information. The entire screening visit itself should last up to 3 hours with patient and caregiver.
- **Intervention/Treatment:** Participants will receive iTBS immediately following screening, should they be determined eligible. Treatment visits will last 20 days, Monday-Friday for approximately 10 minutes each session. Although the actual procedure takes 3 minutes, we estimate close to 5-7 minutes will be required for setting up the treatment and the equipment. Treatment will occur over a 4-week period. Once per week, additional cognitive and safety assessments will be performed. During the last the day of the treatment phase, efficacy and safety scales will be performed also. Subjects will continue to receive routine psychiatric care from their outpatient mental health team, which may consist of a psychiatrist and a therapist.

- **Follow up:** There will be 3 follow up appointments to evaluate long-term efficacy and safety at 1 week, 4 weeks, and 12 weeks since the last treatment session.
- **Unscheduled Visits:** These will be done for any safety concerns and may include any of the assessments listed above. If pregnancy is suspected, another urine pregnancy test will be performed.

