6.2 Secondary Endpoint

- To evaluate the reduction of suicidality in adolescents with MDD: This will be done with descriptive and repeated measures ANOVA.
- To assess durability of antidepressant effect: This will be done with descriptive and repeated measures ANOVA.
- To evaluate the change in Non-suicidal Self Injurious Behavior (NSSIB): This will be evaluated with descriptive statistics.
- Evaluation of adverse events will be performed at every visit and documented according to GCP guidelines. Appropriate follow up and referrals will be made as needed.

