6.3 Statistical Methods

- **Baseline Data:** CDRS-R, HAM-D, and other cognitive and safety assessments will be used at screening to capture baseline data.
- **Efficacy Analysis:** As this is an uncontrolled study design, the investigators understand that any change in scores or observed improvement in symptoms may not be necessarily attributable to the treatment received. Thus, efficacy analysis will be described in this context. The investigators feel that a larger study would be indicated which may be sham controlled. Repeated measures ANOVA will be used to compare depression rating scores from each of the treatment weeks compared to baseline, as well as comparing scores between follow up visits and baseline and end of treatment weeks. Pearson's r coefficient will be used to determine correlation between, CSSR-S scores, and primary endpoints (CDRS-R & HAM-D). Descriptive statistics to identify if NSSIB is present since the subject's last visit at baseline, during the interventional period and follow ups, will be used. It is worth noting that use of ANOVA analysis has been recommended by a biostatistician, but due to a small sample size, longitudinal data will not have adequate statistical power. In addition, confidence intervals will be large and results will be uninformative regarding statistical power. This uncertainty may contribute to a future study sample size that is still too small for statistical power, but a larger sample size than this protocol.
- **Pharmacokinetic Analysis:** N/A
- **Safety Analysis:** Measurement of safety is a continuous process starting with screening. Medical review of symptoms occurs at every visit. In addition, should safety concerns related to study treatment occur, additional unscheduled safety visits can be performed. Additional assessments are done weekly during the 4-week treatment phase.
- **Personnel:** Study coordinator will complete data entry into RedCap system and oversee data management. The Principle Investigator will do oversight. A TraCS biostatistician ([name]) will complete data analysis and computations and will work with the study team throughout the duration of study activities and completion.

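### Section 6.1 divides the CDRS-R and HAM-D differences by an unnamed standard deviation with no small-sample correction; at n=5 the ratio overstates by 25% on average if the SD of changes is used

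*Combined protocol and SAP*

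**What the plan says.** Section 6.1 is the only place that defines the effect size: "Differences in CDRS-R and HAM-D scores will be divided by the standard deviation for effect size". The parenthesis that follows, "which will not be scaled for statistical significance given the sample size", is about significance; it neither identifies the SD nor corrects the ratio. The synopsis and sections 2.0, 6.2, 6.3 and 6.4 add nothing on either matter.

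The comparison intended is clearer than the denominator:
- The synopsis says "We will compare pre- and post-treatment measures of depression in all subjects with repeated ANOVA measures".
- Section 1.2 speaks of ratings "before and after 4 weeks of treatment, as well as 12 weeks following treatment".
- Aim 1 in 2.0 is "estimating the magnitudes of pre-regimen vs. post-regimen longitudinal changes in CDRS-R, HAM-D, and NSSIB evaluations".
- Section 3.1 places a rating at the close of treatment: "During the last the day of the treatment phase, efficacy and safety scales will be performed also".
- Section 6.2 makes durability secondary: "To assess durability of antidepressant effect: This will be done with descriptive and repeated measures ANOVA".

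Together these point to baseline versus end of treatment (V21), although no section labels that visit as primary.

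On precision, 6.3 warns that intervals will be wide and adds "This uncertainty may contribute to a future study sample size that is still too small for statistical power". Section 6.4 promises a confidence interval for every estimate. The planned sample is five (3.3, 6.4). Section 4.7 rules out replacing subjects who discontinue, and has the scales repeated at a termination visit if the patient agrees.

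**The concern.** The study is not powered for a test, so the estimated size of the change is its main efficacy result. An SD from five subjects is a poor divisor. It is often too small, and dividing by a value that is too small inflates the ratio more than dividing by one that is too large shrinks it. The average ratio therefore lies further from zero than the true one. A wide interval tells the reader that the estimate is uncertain; it does not say that the point estimate leans one way.

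The missing name adds a second problem. The SD of changes, of baseline scores, of pooled pre/post scores, the ANOVA error SD and an outside SD all fit the wording of 6.1, and they give different figures from the same data. The study is open label, so a choice made after the scores are known would be hard to defend. Sections 3.3 and 6.4 say the data will support R01 applications, so the figure is likely to be read outside the study team.

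**Working it through.** **Inputs.** From the documents: n=5; no replacement, so n=4 is possible; baseline plus four weekly and three follow-up ratings, eight in all (5.1, Appendix B). The documents give no SD, pre-post correlation or expected effect, so there is no plan figure to reproduce. Assumed: normal scores, equal pre and post SDs, correlation 0.2 to 0.8, true standardised change d from 0.5 to 2.0.

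**Step 1: mean bias.** Under normality the mean change is independent of the sample SD, so the expected ratio is d/J(df), where

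J(df) = Γ(df/2) / [√(df/2) · Γ((df−1)/2)].

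- n=5, df=4: J = 1/(1.4142 × 0.8862) = 0.798; 1/J = 1.253, an excess of 25%.
- n=4, df=3: J = 0.8862/1.2247 = 0.724; 1/J = 1.382, an excess of 38%.

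This holds for the SD of changes. The baseline SD also has 4 df, which gives 25%, but only approximately, because the entry thresholds in 3.4 make a normal baseline doubtful. For the pooled SD, √[(s₁²+s₂²)/2], simulation gives mean ratios of 1.11, 1.13 and 1.18 at correlation 0.2, 0.5 and 0.8. For the ANOVA error SD with eight complete ratings and compound symmetry, df = (5−1)(8−1) = 28, J = 0.973, and the excess is about 3%. An outside SD gives none.

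**Step 2: median and spread (SD of changes, n=5).** The median ratio to the truth is 1.07 to 1.08, so the median excess is 7 to 8%. At d=1.0 the central 95% of estimates runs from 0.13 to 3.45.

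**Step 3: what the correction does (SD of changes, n=5).** From the noncentral-t moments, mean squared error is 0.400 + 0.493d² uncorrected and 0.255 + 0.273d² corrected.

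| d | RMSE uncorrected | RMSE corrected | Median absolute error uncorrected | Median absolute error corrected |
|---|---|---|---|---|
| 0.5 | 0.723 | 0.568 | 0.35 | 0.30 |
| 1.0 | 0.945 | 0.727 | 0.41 | 0.38 |
| 1.5 | 1.229 | 0.932 | 0.49 | 0.49 |
| 2.0 | 1.541 | 1.161 | 0.589 | 0.604 |

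For d from 0.5 to 1.5, RMSE falls by 21 to 24%, the corrected median is 0.798 × (1.07 to 1.08), about 14 to 15% below the truth, and 57 to 62% of corrected estimates fall below it.

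**Step 4: which SD.** The mean difference is common to every version, so the ratio of two effect sizes is the inverse ratio of their SDs. In 300,000 simulated sets of five, the larger of the baseline-SD and change-SD effects exceeds the smaller by a median factor of 1.40, 1.37 and 1.66 at correlation 0.2, 0.5 and 0.8. At 0.5 the interquartile range is 1.16 to 1.74. Part of the gap is a different target: for a true change of one baseline SD, the change-SD effect is 1/√(2−2ρ) = 0.79, 1.00 or 1.58 at those correlations. At 0.5 the targets coincide and the gap is sampling noise.

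**Step 5: the interval.** For an observed ratio of 1.0 with the SD of changes, the corrected value is 0.80 with a noncentral-t 95% interval of −0.14 to 2.07 at n=5, and 0.72 with −0.29 to 2.20 at n=4.

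**The case against.** The case for leaving 6.1 alone has weight. The plan is candid: 6.3 says change may not be attributable to treatment and that intervals will be wide, 6.4 promises intervals, and 6.3 assigns the analysis to a biostatistician. The correction is a convention. It centres the mean but moves the median from 7 to 8% above the truth to 14 to 15% below, and at true effects of 2 or more it slightly worsens median absolute error. Beside a sampling range of 0.13 to 3.45, a 25% bias is modest.

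All of that stands as a limit on the size of the point, but it does not remove it. Intervals address width, and no interval can be computed for a ratio whose denominator is undefined. The gain in root-mean-square error holds at every effect tabulated. Preferring the SD of changes to a baseline or pooled SD is a matter on which statisticians differ, so no single choice is required.

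Two stronger readings are tempting. A reader might infer that the choice of SD typically changes the result by a factor of 1.5 to 1.8. That band is roughly the range of medians for the largest over the smallest of three SDs (1.47 to 1.75 here). Only 20 to 25% of simulated trials fall inside it, and no document figure supports it. A reader might also infer that the inflated figure will undersize a later trial. No section says this effect size will be used for that, and a single-arm pre-post effect is not a between-group effect.

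**Conclusion.** The point holds at modest size. Section 6.1 plans an uncorrected ratio which, under normality at n=5, is too large on average by 25% with the SD of changes, about 25% with the baseline SD and 11 to 18% with a pooled SD. With the SD of changes the mean excess is 38% at n=4, and the median excess at n=5 is only 7 to 8%. The bias would be about 3% with the ANOVA error SD and nil with an outside SD, so its size depends on a choice the plan has not made. That missing name is itself only an omitted detail; the factor of about 1.4 between baseline-SD and change-SD effects illustrates its consequence under assumed correlations and equal SDs. Neither 6.3 nor 6.4 covers the bias. The point makes no claim about the sample size of any later study.

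**What to change.** In 6.1, state the comparison (baseline to end of treatment, V21) and name one SD in advance. The SD of the paired changes is one defensible choice. For CDRS-R and HAM-D separately, report the raw mean change with its t-based 95% interval, which 6.4 already implies. Beside it, report the mean change divided by that SD and multiplied by the correction for the number analysed (0.798 at n=5, 0.724 at n=4), with a noncentral-t 95% interval for the true effect. If another SD is named, the correction and the interval method must match it; those given here are for the SD of changes.

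The cost is one or two sentences and no new data. The reported effect is about 20% smaller at n=5 (1 − 0.798) and 28% smaller at n=4 (1 − 0.724). Because the corrected median lies about 14% below the truth at n=5, the corrected figure should never appear without its interval.

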6.2 Secondary Endpoint

- To evaluate the reduction of suicidality in adolescents with MDD: This will be done with descriptive and repeated measures ANOVA.
- To assess durability of antidepressant effect: This will be done with descriptive and repeated measures ANOVA.
- To evaluate the change in Non-suicidal Self Injurious Behavior (NSSIB): This will be evaluated with descriptive statistics.
- Evaluation of adverse events will be performed at every visit and documented according to GCP guidelines. Appropriate follow up and referrals will be made as needed.

6.3 Statistical Methods

- **Baseline Data:** CDRS-R, HAM-D, and other cognitive and safety assessments will be used at screening to capture baseline data.
- **Efficacy Analysis:** As this is an uncontrolled study design, the investigators understand that any change in scores or observed improvement in symptoms may not be necessarily attributable to the treatment received. Thus, efficacy analysis will be described in this context. The investigators feel that a larger study would be indicated which may be sham controlled. Repeated measures ANOVA will be used to compare depression rating scores from each of the treatment weeks compared to baseline, as well as comparing scores between follow up visits and baseline and end of treatment weeks. Pearson's r coefficient will be used to determine correlation between, CSSR-S scores, and primary endpoints (CDRS-R & HAM-D). Descriptive statistics to identify if NSSIB is present since the subject's last visit at baseline, during the interventional period and follow ups, will be used. It is worth noting that use of ANOVA analysis has been recommended by a biostatistician, but due to a small sample size, longitudinal data will not have adequate statistical power. In addition, confidence intervals will be large and results will be uninformative regarding statistical power. This uncertainty may contribute to a future study sample size that is still too small for statistical power, but a larger sample size than this protocol.
- **Pharmacokinetic Analysis:** N/A
- **Safety Analysis:** Measurement of safety is a continuous process starting with screening. Medical review of symptoms occurs at every visit. In addition, should safety concerns related to study treatment occur, additional unscheduled safety visits can be performed. Additional assessments are done weekly during the 4-week treatment phase.
- **Personnel:** Study coordinator will complete data entry into RedCap system and oversee data management. The Principle Investigator will do oversight. A TraCS biostatistician ([name]) will complete data analysis and computations and will work with the study team throughout the duration of study activities and completion.

- Missing Data and Protocol Violations: Data will be collected in multiple formats – on paper and later electronically. Paper data will include various scales and assessments. There will be two members of the investigation team during assessments and scale administration, which can assist with looking over the data. Paper documents will be labeled without any personal health information or other sensitive identifying information outside of the study team. These documents will be stored in a locked cabinet in a locked office. If there is any missing data, we will refer to the stored paper documents. If data continues to be missing, we are planning to mitigate selection bias by remarking clearly in our results and discussion that consideration must be given to this fact. Any protocol violations will be assessed by the Principal Investigator, will be submitted to the IRB, and a discussion will be had on how to proceed with the study.
- Other: For any missing data, rationale and documentation will be provided in the database (RedCap) and source documentation.

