5.2 Efficacy Evaluation

Children’s Depression Rating Scale Revised (CDRS-R) – This is one of the most commonly used assessment tools for pediatrics when identifying depression. It assesses symptom severity and can be administered filtered or unfiltered (in context of mood disorder or not). [28] It is a semi structured interview scale. 17 items are scored, with 3 of these 17 being made from observation versus verbal response [28]. This will evaluate overall wellness to determine efficacy of treatment, measuring sleep, appetite, socialization, school/work functioning, and overall wellness. This is a scaled and scored assessment and is filtered.

Hamilton Depression Rating Scale (HAM-D) – This is the most widely used tool to evaluate depression. Interrater reliability is high at 0.97-0.98. It is easily administered and measures severity of depression. It is considered the “gold standard” when assessing depression. There are 21 items to score however only the first 17 are actually totaled, each question has a scaled answer. [29] The HAM-D used in this protocol is the same tool used for routine clinical services in the Department of Psychiatry at UNC. This will also evaluate overall wellness to determine efficacy of treatment, measuring sleep, appetite, socialization, school/work functioning, and overall wellness. This is a scaled and scored assessment.

SITBI (Self-Injurious Thoughts and Behaviors Interview) short form & semi structured interview – Self-injurious thoughts and behaviors, lifetime and past month will be assessed using the Self-Injurious Thoughts and Behaviors Interview (SITBI) short form, a clinician-administered interview (3-10 min) that assesses the presence, frequency, severity, age-of-onset, and other characteristics of a broad range of self-injurious thoughts and behaviors. The SITBI has strong convergent validity, inter-rater reliability ($K = .90$), and test-retest reliability ($K = .70$). [30] It is a comprehensive assessment that is recommended for use in clinical and research settings. [30] This is a descriptive, yes/no assessment.

Other: Patient/Caregiver Satisfaction questionnaire: This is an original, brief questionnaire using scaled and open ended questions that is self-reported. This will gather information on what the participants found helpful and what could be improved for future studies. This questionnaire was created in collaboration and upon request of the funding source Center for Health Innovation.

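### The only NSSIB variable the plan defines is present/absent since the last visit, although Aim 1 asks for the magnitude of change and the SITBI is described as assessing frequency and severity

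*Combined protocol and SAP*

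**What the plan says.** Section 2.0 sets Aim 1 as "estimating the magnitudes of pre-regimen vs. post-regimen longitudinal changes in CDRS-R, HAM-D, and NSSIB evaluations". Hypothesis 3 under that aim expects that adolescents "who demonstrate NSSIB at the start of the trial will show reduction in NSSIB after iTBS treatments".

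Section 5.2 says the SITBI "assesses the presence, frequency, severity, age-of-onset, and other characteristics of a broad range of self-injurious thoughts and behaviors", over lifetime and past-month windows. The same paragraph ends: "This is a descriptive, yes/no assessment".

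The analysis text appears in three places:

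- Section 6.3, Efficacy Analysis: "Descriptive statistics to identify if NSSIB is present" since the last visit, at baseline, during treatment and at follow-up.
- Section 6.2: "To evaluate the change in Non-suicidal Self Injurious Behavior (NSSIB): This will be evaluated with descriptive statistics". No variable or summary measure is named.
- Synopsis, Statistical And Analytic Plan: Pearson's r "coefficient for correlation between Non-suicidal Self Injurious Behavior (NSSIB), depression, and suicidality changes". The scale of the NSSIB change is not given. The corresponding sentence in 6.3 correlates C-SSRS scores with CDRS-R and HAM-D and does not name NSSIB.

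Appendix B schedules the NSSIB interview and SITBI at 8 visits: screening, the end of each of the four treatment weeks, and three follow-ups. Section 3.4 does not require NSSIB for entry and concedes that data on it may be sparse.

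**The concern.** The aim concerns an amount and the defined variable is a state. An analyst who follows 6.3 would produce a yes/no table by visit. A subject who goes from many episodes a week to a few, or from a few to many, has the same entry before and after.

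Hypothesis 3 makes this sharper because it is confined to subjects who are positive at the start. From a baseline of yes, a later code can only be unchanged or better.

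NSSIB is in the study title, Aim 1 and the secondary endpoints, and the synopsis lists it among the safety evaluations. Section 3.4 says the data are meant to justify a larger study of this question. Planning that study needs frequencies and their change, which a yes/no table does not supply.

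**Working it through.** The plan states no numerical figure for NSSIB, and N = 5 rests on logistics and caution, so there is nothing to reproduce. The check compares the passages, then works through the code, then gives an illustration.

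**1. Where is the NSSIB scale defined?**

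| Place | Content on NSSIB | Scale for analysis |
|---|---|---|
| 2.0, Aim 1 | magnitude of change | none given |
| 2.0, Hypothesis 3 | reduction in baseline-positive subjects | none given |
| 5.2 | instrument assesses presence, frequency, severity | format label yes/no |
| 6.2 | change, described | none given |
| 6.3, descriptive sentence | present since last visit | yes/no |
| 6.3, correlation sentence | NSSIB not named | not applicable |
| Synopsis | Pearson's r on changes | none given |

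No passage defines a count, frequency, severity score or change score. Pearson's r does not imply one, since it can be computed on a binary change.

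**2. What the code can show.** Baseline yes leads to yes (unchanged) or no (improved). Baseline no leads to no (unchanged) or yes (new onset). Worsening is therefore not a possible result for a baseline-positive subject. This needs no model.

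**3. How often a real change is coded present both times.** Assumptions, none from the documents: Poisson episodes at weekly rate r, one-week windows, independent periods. P(present) = 1 − exp(−r), and P(present both times) is the product.

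| Rate before → after, per week | Change | P before | P after | Product |
|---|---|---|---|---|
| 8 → 1 | −88% | 0.9997 | 0.632 | 0.63 |
| 4 → 2 | −50% | 0.982 | 0.865 | 0.85 |
| 3 → 1 | −67% | 0.950 | 0.632 | 0.60 |
| 2 → 10 | +400% | 0.865 | >0.999 | 0.86 |
| 1 → 0.125 | −88% | 0.632 | 0.118 | 0.07 |

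The same proportional fall is hidden about 63% of the time from 8 per week and about 7% from 1 per week.

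**4. Do repeated visits help?** With four weekly treatment interviews and a steady rate, P(present at all four) = (1 − exp(−r))⁴. This is 0.632⁴ = 0.16 at 1 per week, 0.865⁴ = 0.56 at 2, and 0.982⁴ = 0.93 at 4. Counting positive visits carries some information at low rates and little at high ones. The plan does not specify such a count.

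**5. Unequal windows.** Follow-ups at 1, 4 and 12 weeks after the last treatment give gaps of 1, 4 − 1 = 3 and 12 − 4 = 8 weeks. With P = 1 − exp(−r × weeks) and an unchanged assumed rate of 0.5 per week, P(present) is 0.39 over 1 week, 0.78 over 3, 0.86 over 4 (about the past-month window) and 0.98 over 8. The code can move although the behavior has not, so any frequency should be expressed per unit of time.

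**The case against.** The strongest reply is that the plan is under-specified rather than confined to a binary analysis. Section 6.2 promises a description of change without limiting it to presence, and the synopsis plans a correlation on NSSIB changes. That stands: a reader might infer that NSSIB is treated as yes/no throughout, and the documents do not say so. These passages make the plan inconsistent, but they supply no quantitative variable.

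The yes/no label in 5.2 is weak evidence. Section 5.1 labels the C-SSRS almost identically, yet 6.2 plans repeated measures ANOVA for suicidality and 6.3 uses C-SSRS scores. The label does not fix the analysed variable, so the weight falls on 6.3.

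A reader might also infer that escalating self-injury would go unseen. Sections 5.1 and 9.0 provide adverse event and symptom review at every visit, and the log in Appendix C calls for entries when severity increases or a pre-existing condition worsens. NSSIB is not named there, but a recording route exists. The 6.3 summary is also not restricted to baseline-positive subjects, so new onset would already show.

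Finally, 5.2 says frequency is assessed. It does not establish that a count per visit interval is already taken. With N = 5, and NSSIB described in 3.4 as exploratory, the practical weight is limited. Both points are fair, but a per-subject listing does not depend on power.

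**Conclusion.** The concern holds as a mismatch between Aim 1 and the one NSSIB variable the plan defines. It is more than missing detail, because following 6.3 as written codes any rise or fall between non-zero levels as unchanged and leaves worsening in baseline-positive subjects outside the NSSIB result. That part rests on the text alone.

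The size is uncertain. The probabilities rest on assumed Poisson episodes, one-week windows and chosen rates, while the documents give neither a rate nor an expected number of subjects with NSSIB at baseline (0 to 5 are possible). The loss is large when self-injury is frequent and small when it is rare, so no single miss rate should be quoted.

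Two further inferences go too far. Aim 1 as a whole is not unanswerable, since CDRS-R and HAM-D have effect sizes and repeated measures ANOVA. Hypothesis 3 is not wholly untestable either, since cessation, or fewer positive visits, would count as partial evidence of reduction.

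**What to change.** In sections 6.2 and 6.3, name SITBI NSSIB frequency as the variable for Aim 1 and Hypothesis 3.

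- Record each frequency with the interval it covers: past month at baseline, and since the last visit thereafter. This reconciles the windows in 5.2 and 6.3. Express it per week.
- List it per subject at each of the 8 scheduled interviews, with change from baseline.
- Flag any increase and any new onset.
- Keep presence/absence as a supporting line.
- Align the synopsis, 5.2 and 6.2 with this, including the yes/no label and whether NSSIB enters the correlation.

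The cost is plan wording and possibly one numeric database field. If the interview form captures only past-month frequency, the recall wording at later interviews must be changed to match the interval; otherwise weekly answers overlap. No new visit, instrument or subject is required.
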